22.3 Secondary Study Endpoints

State the secondary endpoints to be measured in the study.

- 3) To what degree does presence in the virtual reality environment impact the efficacy of the VRET scripts?
- 4) How do users rate the acceptability of treatment delivered through virtual reality?

2.0 Background

2.1 Scientific Background and Gaps

Describe the scientific background and gaps in current knowledge.

Social Anxiety Disorder (SAD) has a lifetime prevalence of 12.1% in the U.S. population of adults (Kessler & Wang, 2008). According to the Diagnostic and Statistical Manual of Mental Disorders (5th ed.; DSM-5; American Psychiatric Association, 2013), SAD is characterized by an intense fear of social and performance situations or the fear of acting in an embarrassing way due to apprehension about negative evaluation by others. This can lead to marked avoidance of routine situations such as going to the grocery store, making appointments, or socializing with others resulting in significant impairment. SAD may also affect individual's ability to succeed professionally. For individuals with job interview anxiety, it is well documented that high levels of anxiety may result in a low job interview score that negatively impacts an applicant's chances of getting hired (McCarthy & Goffin, 2004). Cook, Vance and Spector (2000) provided evidence that it is more likely for individuals with a high level of job interview anxiety to receive significantly lower performance ratings and less likely to be offered a second-round interview and subsequent job offer. As a result, individuals with job interview anxiety may experience significant vocational impairment even when they may display superior on-the-job performance. To meet the needs of this population, the gold standard for treatment is exposure therapy.

2.2 Previous Data

Describe any relevant preliminary data.

Exposure therapy is an evidence-based treatment for social anxiety that has been shown to effectively target the fears of negative evaluation that is characteristic of SAD (Emmelkamp, 2005). Despite rates of success, there are logistical barriers of exposure therapy that limit treatment acceptability and accessibility (Olatunji, Deacon, & Abramowitz, 2009). Therefore, there is opportunity for growth and innovation for exposure therapy to expand the reach of treatment.

Virtual reality has been shown to meet these increased demands. Through this technology, experimenters can control every variable presented in a given virtual social scenario, which is not feasible in the real world. Further, it is less cost prohibitive, as the user can virtually experience a large array of social situations, regardless of distance or financial means. Virtual reality exposure therapy (VRET) has been shown to be as effective, and in some cases marginally more effective, than real-life exposure therapy for anxiety disorders (Powers & Emmelkamp, 2008). Preliminary results from VRET studies have also been promising for treating social anxiety, with participants maintaining treatment gains at a one-year follow-up (Anderson et al., 2013).

2.3 Study Rationale

Provide the scientific rationale for the research.

There is a dearth of studies testing the efficacy of virtual reality exposure therapy scripts based on its level of realness. Our study attempts to fill this gap by making the interactions and scenes inside the virtual reality exposure therapy scripts as realistic to everyday encounters.

The goal of the current study is to leverage the capabilities of this virtual reality technology to create a more immersive experience in social exposures. Individuals who experience a difficult time building social relationships, accomplishing everyday tasks, or pursuing interviews can practice those same behaviors in a controlled environment. The current study allows for a high degree of researchers' control to effectively and repeatedly create "social mishap" exposures, which is generally not feasible in the real world. We are hopeful that this study will not only increase the accessibility and utility of social phobia treatment, but also contribute to the expanding evidence-base for digital mental health interventions.

This study will focus on the effectiveness of the exposure therapy scripts to help people with social phobia. Individuals will be excluded if their symptoms would be best treated in a different setting, if we

are not equipped to offer needed treatment, or if the person is not able or interested to participate in treatment.

3.0 Inclusion and Exclusion Criteria

Create a numbered list below in sections 3.1 and 3.2 of criteria participants must meet to be eligible for study enrollment (e.g., age, gender, diagnosis, etc.). Indicate specifically whether you will include any of the following vulnerable populations: (You may not include members of these populations as participants in your research unless you indicate this in your inclusion criteria.) Review the corresponding checklists to ensure that you have provided the necessary information.

- **Adults unable to consent**
 - Review “CHECKLIST: Cognitively Impaired Adults (HRP-417)” to ensure that you have provided sufficient information. HRP-417 can be accessed by clicking the Library link in CATS IRB (<http://irb.psu.edu>).
- **Individuals who are not yet adults (infants, children, teenagers)**
 - If the research involves persons who have not attained the legal age for consent to treatments or procedures involved in the research (“children”), review the “CHECKLIST: Children (HRP-416)” to ensure that you have provided sufficient information. HRP-416 can be accessed by clicking the Library link in CATS IRB (<http://irb.psu.edu>).
- **Pregnant women**
 - Review “CHECKLIST: Pregnant Women (HRP-412)” to ensure that you have provided sufficient information. HRP-412 can be accessed by clicking the Library link in CATS IRB (<http://irb.psu.edu>).
- **Prisoners**
 - Review “CHECKLIST: Prisoners (HRP-415)” to ensure that you have provided sufficient information. HRP-415 can be accessed by clicking the Library link in CATS IRB (<http://irb.psu.edu>).
- **Neonates of uncertain viability or non-viable neonates**
 - Review “CHECKLIST: Neonates (HRP-413)” or “CHECKLIST: Neonates of Uncertain Viability (HRP-414)” to ensure that you have provide sufficient information. HRP-413 and HRP-414 can be accessed by clicking the Library link in CATS IRB (<http://irb.psu.edu>).

3.1 Inclusion Criteria

List the criteria that define who will be included in your study.

- 1) Be at least 18 years old.
- 2) Meet criteria on the 15- to 25-minute MINI Neuropsychiatric Interview (Sheehan et al., 1997) for a social anxiety disorder.
- 3) Not psychotic via the MINI.
- 4) Not actively suicidal via the MINI (i.e. Participants who endorse suicidal intent and/or plan to commit suicide).
- 5) Not actively homicidal via a single question (i.e., “Have you had the urge to hurt someone else within the past two weeks?”)
- 6) Not needing immediate medical attention for ongoing alcohol or substance use via the MINI.
- 7) Dual diagnoses apart from psychosis, alcohol or drug use disorders, are allowed.
- 8) Not judged to have severe mental illness better treated through broader mental health services that can be offered through our clinic (for example, individuals who require more than once-weekly sessions, individuals who require medical monitoring).
- 9) Able to read, write, and understand English.

3.2 Exclusion Criteria

List the criteria that define who will be excluded in your study.

- 1) Not interested in engaging in mental health treatment, or seeking mental health treatment for concerns unrelated to symptoms of social anxiety via two questions (i.e., “Are you currently interested in seeking mental health treatment to manage social anxiety symptoms better?” and “Are you currently interested in seeking mental health treatment to manage symptoms other than social anxiety?”)
- 2) Individuals not meeting criteria on the MINI Neuropsychiatric Interview (Sheehan et al., 1997) for a social anxiety disorder.
- 3) Those who do not meet the inclusion criteria.

3.3 Early Withdrawal of Participants

3.3.1 Criteria for removal from study

Insert subject withdrawal criteria (e.g., safety reasons, failure of subject to adhere to protocol requirements, subject consent withdrawal, disease progression, etc.).

1. If a participant no-shows to 4 sessions in a row or 6+ sessions in a 2-month period.
2. If a participant’s symptoms increase to the point that more intensive care than can be provided through this study is required.

3.3.2 Follow-up for withdrawn participants

Describe when and how to withdraw participants from the study; the type and timing of the data to be collected for withdrawal of participants; whether and how participants are to be replaced; the follow-up for participants withdrawn from investigational treatment.

Participants are free to withdraw from the study at any point in time. Data will be collected up to the point the participant expresses his/her wish to withdraw. If a subject withdraws from the study, we will not ask participants to continue with study procedures (post and follow-up assessments). Further, as per FDA regulations, we will not remove study data collected up to the point of withdrawal.

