After self-report questionnaires are completed, participants will then complete the baseline clinical interview (paper version of “LIMBIX - Measure - MINI Neuropsychiatric Interview.pdf”) conducted by a study team member who is not the ultimate research therapist. The clinical interview will generally take about 15 to 25 minutes. This interview will be videotaped to conduct reliability assessment on the diagnoses.

Participants who meet the study eligibility criteria will next be contacted by phone by another study team member within a week to receive their random assignment to either the virtual reality exposure therapy condition or the waitlist control condition and to schedule their treatment planning session. Participants in the immediate treatment group will be invited to start treatment soon after the baseline assessments, whereas those in the waitlist control condition will be invited to start this treatment 8 weeks later. The script “LIMBIX - Scripts - Study Therapist to Subject” will be used to facilitate this process.

Within a day the intake assessor completes the initial assessment for an eligible participant, the coordinator will (1) randomly assign the eligible participant who had just completed the interview to their treatment condition, (2) call the participant to inform them of their study condition, and (3) inform their research therapist assigned to be in charge with conducting the 8 to 10 50-minute weekly treatment planning and therapy sessions.

As participants assigned to the treatment condition will begin therapy immediately, the coordinator will communicate this message to the research therapist within a day of the initial assessment.

On the other hand, participants assigned to the waitlist control condition will begin therapy 8 weeks later, and the coordinator will communicate this message within a few weeks after the initial assessment visit.

Once the research therapist receives the message from the coordinator to start scheduling treatment with a particular participant, he or she is expected to contact the participant and set up an appointment within the next one or two weeks depending on their availability.

Step 3: Treatment Planning

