8.3 Statistical methods

Describe the statistical methods (or non-statistical methods of analysis) that will be employed.

We will conduct a series of growth curve analyses to test for treatment efficacy. We will use the R packages 'lme4' (Bates, Maechler, & Bolker, 2012), 'lmerTest' (Kuznetsova & Brockhoff, 2014), and 'lavaan' (Rosseel, 2012) to calculate the growth trajectories for each participants. We will test for the impact of time using participants' scores at post-treatment, and at 6-month and 12-month follow-ups. We intend to perform separate models for each of the study outcome measures.

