Participants involved in this study will be asked to discuss difficult topics including current symptoms, past trauma, substance use, and psychiatric history. Despite the discomfort this may cause, this risk remains minimal as the procedures involved in the study are similar to those that individuals would encounter when engaging in any other mental health treatment.

Circumstances under which the study will be ended to prevent future risk:

The study will be ended if the protocol is shown to cause unnecessary harm to participants without any compensatory benefit. The Beck Anxiety Inventory (BAI; Beck & Steer, 1993) will be used to assess changes in symptoms every week. If no response, or negative response, (as operationalized as a 15% increase in severity on BAI scores for two consecutive sessions after initial adjustment to treatment has been made) continues for at least 5 participants, or if at least 5 participants are referred out due to requiring more care, the study will be stopped. This figure was chosen as controlled studies of single-diagnosis treatment trials often show that 5-10% of the study populations may exhibit an increase in symptoms while participating in a therapy study and 35- 40% report little benefit (Hansen, Lambert, & Forman, 2002). Given that the community population served by this study may be more complex than the populations seen in clinical trials the number was slightly increased.

It is expected that some participants will see a temporary increase in symptoms over the course of treatment due to the need to discuss difficult emotional information in treatment. To help ensure that any of the participant's concerns are addressed and that the treatment offered is responsive to the participant's needs, ongoing symptom monitoring will assist with the identification of individuals who do not appear to be benefiting from treatment and adverse effects will also be monitored through the assessment process (i.e., through the use of the Negative Effects Questionnaire; Rozental, Kottorp, Boettcher, Andersson, & Carlbring, 2016). This monitoring will also allow for a collaborative discussion with study participants so that adjustments can be made in their treatment as needed. If an individual participant becomes an imminent risk to themselves or others, their participation in the study will end and they will be referred to an appropriate level of care. We will ask such

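### Participants who withdraw, and apparently those removed for missed sessions, are not assessed at post-treatment or follow-up, which puts the VRET-waitlist contrast at risk of bias, probably towards VRET

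*Combined protocol and SAP*

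**What the plan says.** Section 3.3 (Early Withdrawal of Participants) has two parts. Section 3.3.1 lists two criteria for removal from the study, not merely from treatment. The first is missed sessions: "If a participant no-shows to 4 sessions in a row or 6+ sessions in a 2-month period". The second is that "symptoms increase to the point that more intensive care than can be provided through this study is required".

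Section 3.3.2 then covers follow-up. It says "Data will be collected up to the point the participant expresses his/her wish to withdraw", and that for someone who withdraws "we will not ask participants to continue with study procedures (post and follow-up assessments"). Data already in hand are kept: "we will not remove study data collected up to the point of withdrawal". It does not mention participants whom the team removes, and it does not distinguish a person who stops attending from one who refuses further contact.

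Section 7.2 ties the post-treatment packet to the final therapy session (Step 7). The 3- and 6-month measures are online self-report, timed from the end of treatment. Between-session symptom measures are taken in treated participants and reach the waitlist only once its treatment has begun (Step 5). On timing, "participants assigned to the waitlist control condition will begin therapy 8 weeks later" (Step 2). No assessment at the end of the wait is described.

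Section 8.3 plans growth curve models of "scores at post-treatment, and at 6-month and 12-month follow-ups". It states no analysis set, no missing-data assumption and no sensitivity analysis.

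**The concern.** Outcomes that are never requested cannot be recovered by any later analysis. Under the plan as written, a VRET participant who leaves before the final session has no post-treatment score, and nothing triggers a later one, because both the packet and the follow-ups are timed from the end of treatment. Section 7.2, Step 4 also foresees discontinuing the intervention because it is unhelpful or causes severe cybersickness. Those reasons arise only with VR and may be related to outcome, and no later assessment of such people is described.

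The loss is unlikely to be balanced. In the 8 weeks before the waitlist starts therapy, only VRET participants have sessions to miss or a VR intervention to stop. If those who avoid exposure do worse, losing them flatters VRET. Hypothesis 1 (efficacy against waitlist) and hypothesis 2 (maintenance at 3 and 6 months) both rest on the scores that would be missing.

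**Working it through.** **The plan's own figure.** Section 8.2 gives 300 + 300 + 150 = 750 at 80% power and two-sided alpha 0.05, but prints no effect size, so the 300 per group cannot be reproduced forwards. Solved backwards with d = (1.96 + 0.842) × sqrt(1/n1 + 1/n2):

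- 300 v 300: d = 0.229
- 300 v 150: d = 0.280
- 600 v 150 (both VRET arms pooled against waitlist): d = 0.256

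The last is the benchmark below, because it matches the contrast in hypothesis 1. Section 8.2 states no allowance for dropout.

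**Inputs not in the documents (assumptions).** p is the share of the VRET arms missing at post-treatment, over and above the waitlist. D is how much worse, in SD, the missing would have scored than those observed. I take p = 10-30% and D = 0.3-0.5.

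**Formulas.** Shift towards VRET = p × D. Standard error = sqrt(1/(600(1 − p)) + 1/150). With no true effect, the two-sided rejection rate is Φ(−1.96 − shift/SE) + 1 − Φ(1.96 − shift/SE).

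| p | D | VRET observed | Shift (SD) | SE | Type I error |
|---|---|---|---|---|---|
| 10% | 0.3 | 540 | 0.03 | 0.0923 | 6.2% |
| 10% | 0.5 | 540 | 0.05 | 0.0923 | 8.4% |
| 20% | 0.3 | 480 | 0.06 | 0.0935 | 9.8% |
| 20% | 0.5 | 480 | 0.10 | 0.0935 | 18.8% |
| 30% | 0.3 | 420 | 0.09 | 0.0951 | 15.7% |
| 30% | 0.5 | 420 | 0.15 | 0.0951 | 35.1% |

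At 20% and 0.5 SD, 0.10/0.256 = 39% of the detectable effect. With D = 0, or with the same p and D in both arms, the shift under the null is zero.

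**How much can come from removal for worsening?** Section 11.0 says that "if at least 5 participants are referred out due to requiring more care, the study will be stopped". So at most 4 such referrals can occur while the study continues. If all 4 fall in the VRET arms, p = 4/600 = 0.67%. In the extreme case that they are the 4 worst outcomes, the shift is φ(z)/(1 − p) with z = 2.475, which is 0.019 SD (type I error 5.5%). This route is minor. Missed sessions and voluntary withdrawal carry the point.

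**The case against.** The strongest reply is that the documents say less than a reader might infer from them. Five inferences are tempting.

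- *Removed participants are never followed.* The sentence in 3.3.2 is written for someone who wishes to withdraw. Its application to removed participants is inferred from the shared heading and from the absence of any trigger for their post packet. It is a likely reading, not a stated rule. Leaving alone people who asked to be left alone is also defensible, and the fix below keeps that.
- *The contrast is biased towards VRET.* This needs a waitlist score taken before the waitlist is treated, and none is described. If waitlist post scores come only from the packet before their own final session, the same removal rules act on both arms and the direction is undetermined. This objection stands: the bias is probable, not shown.
- *Treated participants who get worse drive the bias.* The worsening criterion is not limited to one arm, and the study-level stop caps its effect at about 0.02 SD.
- *This is a completers analysis.* Section 8.3 does not restrict the analysis to completers, and 3.3.2 keeps earlier data. A mixed model could use baseline and session scores. The plan does not say it will, and the waitlist has no session scores during the wait. The accurate description is that the analysis set is unspecified.
- *Acceptability is rated only by those who finish.* Section 7.2, Step 4 collects the System Usability Scale in the first, fourth and last weeks, so early leavers can contribute. Only the final interview is confined to those who reach termination.

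It is also fair to say that nothing in the documents supports a particular loss rate, and that the no-show threshold is demanding in a course of 8 to 10 weekly sessions. At the low end of the assumed range the type I error is only about 6%.

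What survives is the gap itself. Withdrawn participants are not assessed, stopping sessions is not separated from leaving the study, and no analysis set or missing-data plan addresses the loss.

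**Conclusion.** The point holds as a risk of bias in the VRET-waitlist contrast and in the maintenance estimate, probably towards VRET. It does not hold as a demonstrated bias. The no-assessment rule is explicit for participants who withdraw and apparent for those removed.

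The size rests on two assumptions that the documents do not supply. One-sided loss of 10-30%, with outcomes 0.3-0.5 SD worse in those lost, gives a shift of 0.03-0.15 SD and a two-sided type I error of about 6-35% for 600 v 150. The direction rests on a further assumption, that the waitlist is measured before its own treatment, which the plan does not describe.

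It should be fixed before enrolment goes further, because the missing outcomes cannot be restored later and the remedy is cheap.

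**What to change.** 1. In 3.3.2, separate stopping sessions from declining further contact. Send the post, 3-month and 6-month questionnaires online to every randomised participant who has not declined contact. Fix the dates from randomisation or from the planned end of treatment, not from the last session attended.
2. In 7.2, add an end-of-wait online questionnaire for the waitlist before their treatment starts, matched in timing to the VRET assessment it is compared with. The matched date needs stating, because VRET runs for 8 to 10 weekly sessions and the wait is 8 weeks.
3. In 8.3, analyse all randomised participants in their assigned arm with baseline in the model, and add a missing-not-at-random sensitivity analysis. The outcome times there (6 and 12 months) must also be reconciled with those collected under 7.2 (3 and 6 months), which is a separate contradiction.

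The removal rules in 3.3.1 are unchanged.

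The cost is protocol and consent wording, reminder emails and one extra online questionnaire for the waitlist. The 3- and 6-month measures are already online self-report, so no visits are added. The estimated effect may become less favourable.

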4.0 Recruitment Methods

4.1 Identification of participants

Describe the methods that will be used to identify potential participants or the source of the participants. If not recruiting participants directly (e.g., database query for eligible records or samples) state what will be queried, how and by whom.

StudyFinder: If you intend to use StudyFinder (<http://studyfinder.psu.edu>) for recruitment purposes, please indicate this in section 4.1 along with any other methods for identifying participants. Note that information provided in this protocol should be consistent with information provided on the StudyFinder page in your CATS IRB study.

For Penn State Hershey submissions using Enterprise Information Management (EIM) for recruitment, attach your EIM Design Specification form on the Basic Information page in CATS IRB (<http://irb.psu.edu>). See HRP-103 Investigator Manual, “What is appropriate for study recruitment?” for additional information.

For participants we are planning to recruit from the PSU subject pool, we will identify potential participants by using the Social Phobia Diagnostic Questionnaire (“LIMBIX – Screening – SPDQ”) and the Beck Depression Inventory II (“LIMBIX – Screening – BDI-II”). Subject pool participants who screen positive (i.e., they scored >7.38 (85% specificity, sensitivity 82% (Bianca Lauria-Horner, 2016)) on the

SPDQ) and score above 20 on the BDI-II will be invited to an initial appointment to complete the baseline assessments and clinical interview.

For participants we are planning to recruit from the Penn State Psychological Clinic, we aim to reach out to potential clients with social anxiety disorder through these means: (1) Advertising our study at the adult clinic waiting room (see flyer attached at the Appendix); (2) Clients will contact us if they are interested in participating; (3) Therapists will raise awareness to potential clients about our study by giving them the flyer and letting the client contact us if they are interested in participating. Once a client has expressed interest, we will schedule the initial visit comprising baseline assessments to determine their study eligibility.

We also intend to recruit from StudyFinder and will ensure that the information written in this protocol is consistent with that provided on the StudyFinder page of our CATS IRB.

